7.4 Reporting of Pregnancy

Pregnancies (including a positive pregnancy test regardless of age or disease state) of a female participant occurring while the participant is enrolled will result in study cessation for the pregnant participant. The female participant will be referred to an obstetrician-gynecologist. Pregnant dialysis patients require more intensive dialysis therapy and are not appropriate for ongoing study participation. The Investigator will follow the female participant until completion of the pregnancy and must document the outcome of the pregnancy (either normal or abnormal outcome). If the outcome of the pregnancy was abnormal (e.g., spontaneous or therapeutic abortion), the Investigator should report the abnormal outcome as an AE. If the abnormal outcome meets any of the serious criteria, it must be reported as an SAE.

7.5 Stopping Rules

Given that the primary focus of this pilot trial is on safety and tolerability, there are no pre-specified stopping rules for efficacy outcomes. However, the investigators will monitor all safety endpoints for evidence of differential safety effects, and routinely update the safety monitor. The safety monitor may recommend study termination on the basis of unacceptable increases in AEs or external data.

7.6. Data Safety and Monitoring Plan

7.6.1 Overall Framework

There are three different acceptable approaches to data and safety monitoring plans. Monitoring can be conducted by the research team, an independent (external) safety monitor or group, or an independent data safety monitoring board. This study will enroll up to 40 patients and will last for 18 weeks (6 weeks of dose escalation and 12 weeks of subsequent follow-up per participant). Given the small number of participants, relatively short duration of the study, the frequency of study visits (weekly in the first 6-weeks and then every 2 weeks in the latter 12-weeks), the participants' regular contact with medical professionals (three times a week at a dialysis clinic), the lack of blinding, that all activities will take place at a single site (University of North Carolina at Chapel Hill), and that the potential AEs are likely to be mild in nature and detected by study personnel and/or dialysis clinic personnel, we will ensure participant safety through regular review by the research team. This will include review of study progress, listings of AEs, and AE logs. We will also use an independent safety monitor to provide an additional layer of protection.

7.6.2 Monitoring and Frequency

Monitoring by the research team: The PI and study coordinator will maintain non-serious AE and SAE logs and case report forms throughout the study. The research team (study investigators, other significant contributors and research coordinator) will review study records, AEs, and SAEs for all participants on an ongoing basis. The UNC research team includes 1 board-certified nephrologist and a dialysis-trained pharmacist, both with the necessary expertise to assess study AEs. The Principal Investigator (PI) will review all such events every 2 weeks. All accumulated AEs of interest, SAEs,

and data on overall AE rates will be presented at the monthly project team meetings to the broader research team. Review of the data will uncover patterns that might suggest a need for modification of study practices to ensure patient safety. If the research team uncovers such patterns, the safety monitor will be asked to review the events.

The PI and/or research coordinator will report all SAEs to the research team and external safety monitor within 24 hours of becoming aware of the event. The PI and/or research coordinator will report SAEs that are unanticipated and related to the research to the research team, external safety monitor, and institutional review board (IRB) within 24 hours of becoming aware of the event. The PI will personally review all study results and notify participants of any abnormal results, including those present at baseline unrelated to the study intervention to ensure participants are able to seek appropriate medical care.

Monitoring by an external safety monitor: Additional monitoring will be provided by a board-certified adult nephrologist not associated with the study. This external monitor will review all AEs and SAEs in detail including the time of onset, description, severity, time course, duration, outcome, relationship of the AE/SAE to the study drug, and any action(s) taken. The external safety monitor will review AEs and SAEs every 6 months (3 times over the ~18-month study), and SAEs that are unanticipated and related to the research as soon as the research team becomes aware. The monitor will help the research team determine whether further safety guards should be instituted and whether the benefit of the study continues to outweigh potential risks.

Information to be monitored: The research team and external safety monitor will monitor AEs including hypotension, allergic or toxicity-related symptoms (rash, tinnitus, or hearing change), objective hearing change, and electrolyte abnormalities as well as SAEs.

7.7 Medical Emergency Procedures

7.1.1 Hypokalemia management

Serum potassium will be measured weekly during dose escalation and monthly during follow-up. Treating clinicians will manage the dialysate potassium according to clinic standards. Study staff will monitor potassium values and contact treating clinicians in the event of hypokalemia to ensure that hypokalemia is being actively managed. Treating clinicians will be free to manage hypokalemia according to local standards, including changes to the dialysate potassium concentration. However, study drug dose reductions or discontinuation will be directly managed by study investigators. Occurrence of a serum potassium <3.2 mEq/L will end dose titration, and the participant will return to the prior tolerated furosemide dose. If the hypokalemia occurs at the lowest administered dose, furosemide will be stopped and not restarted. Serum potassium will be rechecked within one week when potassium is <3.2 mEq/L. Results of serum potassium will be conveyed to treating clinicians and the dialysis unit nursing staff.

7.1.2 Hypomagnesemia management

Serum magnesium will be measured weekly during dose escalation and monthly during follow-up. Treating clinicians will manage the dialysate magnesium according to clinic standards. Study staff will monitor magnesium values and contact treating clinicians in the event of hypomagnesemia to ensure that hypomagnesemia is being actively managed. Treating clinicians will be free to manage hypomagnesemia according to local standards, including changes to the dialysate magnesium concentration. However, study drug dose reductions or discontinuation will be directly managed by study investigators. Occurrence of a serum magnesium <0.8 mEq/L will end dose titration, and the participant will return to the prior tolerated furosemide dose. If the hypomagnesemia occurs at the lowest administered dose, furosemide will be stopped and not restarted. Serum magnesium will be rechecked within one week when magnesium is <0.8 mEq/L. Results of serum magnesium will be conveyed to treating clinicians and the dialysis unit nursing staff.

7.1.3 Hypocalcemia management

Serum corrected calcium will be measured weekly during dose escalation and monthly during follow-up. Treating clinicians will manage the dialysate calcium according to clinic standards. Study staff will monitor corrected calcium values and contact treating clinicians in the event of hypocalcemia to ensure that hypocalcemia is being actively managed. Treating clinicians will be free to manage hypocalcemia according to local standards, including changes to the dialysate calcium concentration. However, study drug dose reductions or discontinuation will be directly managed by study investigators. Occurrence of a corrected serum corrected calcium <7.0 mg/dL will end dose titration, and the participant will return to the prior tolerated furosemide dose. If the hypocalcemia occurs at the lowest administered dose, furosemide will be stopped and not restarted. Serum corrected calcium will be rechecked within one week when corrected calcium is <7.0 mg/dL. Results of serum corrected calcium will be conveyed to treating clinicians and the dialysis unit nursing staff.

7.1.4 Hypotension management

In the event of serious dialysis-associated hypotension (hypotension requiring hospitalization or treatment in an emergency room and not attributable to overt sepsis, acute myocardial infarction, or other cardiovascular event (e.g. aortic dissection)) study investigators will review the participant's non-study anti-hypertensive medications, estimated dry (target) weight, and volume status. The participant's nephrologist will be contacted to consider the following interventions listed in the preferred order of implementation:

1) Decrease non-study anti-hypertensive medication(s)

2) Increase prescribed dry (target) weight if there is no evidence of peripheral or pulmonary edema

3) Reduce UF rate by increasing dialysis session duration

4) Reduce dose of study drug if there are no other anti-hypertensive medications prescribed OR other anti-

hypertensive medications should not be discontinued (e.g., beta blocker following myocardial infarction) 5) Discontinue study medication at the 3rd dose reduction

Treating clinicians will be free to manage hypotension according to standard clinical practices and are not obligated to follow the study guidelines with respect to non-study medication, fluid removal rate, or dry weight. In contrast, dose reduction or discontinuation of study drug will be directly managed by study staff in accordance with the guideline.

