Occurrence of any of the following events will end dose up-titration: 1) electrolyte abnormalities (serum potassium <3.2 mEq/L, serum magnesium <0.8 mEq/L, and/or serum corrected calcium <7 mg/dL); 2) side effects attributable to furosemide (severe or very severe rash, tinnitus, or hearing change); decrease in Inner Effectiveness of Auditory Rehabilitation (Inner EAR) instrument score by more than 10 points; and/or intradialytic systolic BP <80 mmHg that a study investigator attributes to study drug-induced hypovolemia); and/or 3) patient non-acceptance (defined as the

patient reporting unwillingness to take the study drug). If one of these events occur, the participant will return to the prior tolerated oral furosemide dose. If one of these events occurs at the lowest administered dose, oral furosemide will be stopped and not re-started.

During the 12-week follow-up period (period 2), participants who tolerated and accepted furosemide in period 1 will continue their maximally tolerated period 1 furosemide dose during the 12-weeks of follow-up. If a participant has electrolyte abnormalities or other side effects attributable to furosemide in period 2 (i.e. on their period 1 maximally tolerated dose), the dose will be lowered sequentially (i.e. dose de-escalation: $160 \rightarrow 120 \rightarrow 80$ mg twice daily, or, if on alternative dosing due to prior diuretic use, decrease dose by 50%, rounded to the nearest whole tablet strength of existing (i.e. available) furosemide tablet formulations, until tolerated). If side effects persist or if the participant chooses, oral furosemide will be stopped.

Investigational New Drug (IND) exemption status

Oral furosemide is marketed as a prescription drug product and regulated by the U.S. FDA. Furosemide is indicated for edema and hypertension (signs and symptoms of volume overload). Its use in this study will be considered an on-label use. Our study is exempt from IND requirements for the following reasons:

- Oral furosemide is lawfully marketed in the U.S.
- The study is not intended to be reported to the FDA as a well-controlled study in support of a new indication for use and is not intended to be used to support any other significant change in the labeling for the drug.
- The study is not intended to support a significant change in the advertising for the product.

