4.3 Intervention/Treatment procedures (by visits)

During the 6-week dose titration period (period 1), study drug administration visits will occur every 2 weeks on the first day of the participant's weekly, routinely scheduled HD treatments (i.e. Monday or Tuesday during weeks 0, 2, 4, and 6). During the 12-week follow-up period (period 2), study drug administration visits will occur every 4 weeks on the first day of the participant's weekly, routinely scheduled HD treatments (i.e. Monday or Tuesday during weeks 10, 14 and 18).

Dose-titration (period 1)

Week 0:

A. Participants who are not taking oral furosemide at study entry will receive 2-weeks supply of 80 mg oral furosemide twice daily dosing.

- B. Participants who are taking oral furosemide at study entry will receive 2-weeks supply of his/her prescribed oral furosemide dose.
- C. Participants who are taking another loop diuretic (e.g. bumetanide) at study entry will receive 2-weeks supply of an equivalent dose of furosemide (1mg bumetanide = 40 mg furosemide).

Week 2:

- A. Participants who were not taking oral furosemide at study entry and who tolerated the 80 mg twice daily dose (i.e. no hypokalemia, serious hypotension, symptoms, etc.) will receive 2-weeks supply of 120 mg oral furosemide twice daily dosing.
- B. Participants who were taking oral furosemide at study entry and tolerated the first 2 weeks of dosing will receive 2-weeks supply of furosemide dose 50% higher than initial dose, rounded to the nearest whole tablet strength of existing (i.e. available) furosemide tablet formulations (not to exceed 320 mg/day).
- C. Participants who were taking another loop diuretic at study entry and tolerated the first 2 weeks of furosemide dosing will receive 2-weeks supply of furosemide dose 50% higher than their initial dose, rounded to the nearest whole tablet strength of existing (i.e. available) furosemide tablet formulations (not to exceed 320 mg/day).
- D. Participants who did not tolerate the weeks 0 and 1 dose of furosemide will stop furosemide, and it will not be restarted. See below for parameters for determining intolerance.

Week 4:

- A. Participants who were not taking oral furosemide at study entry and who tolerated the 120 mg twice daily dose (i.e. no hypokalemia, serious hypotension, symptoms, etc.) will receive 2-weeks supply of 160 mg oral furosemide twice daily dosing.

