- B. Participants who were taking oral furosemide at study entry and tolerated the last 2 weeks of dosing will receive 2-weeks supply of furosemide dose 50% higher than initial dose, rounded to the nearest whole tablet strength of existing (i.e. available) furosemide tablet formulations (not to exceed 320 mg/day).
- C. Participants who were taking another loop diuretic at study entry and tolerated the last 2 weeks of furosemide dosing will receive 2-weeks supply of furosemide dose 50% higher than initial dose, rounded to the nearest whole tablet strength of existing (i.e. available) furosemide tablet formulations (not to exceed 320 mg/day).
- D. Participants who did not tolerate the weeks 2 and 3 dose of furosemide will return to the prior tolerated oral furosemide dose. See below for parameters for determining intolerance.

Week 6:

- A. Participants who were not taking oral furosemide at study entry and who tolerated the 160 mg twice daily dose (i.e. no hypokalemia, serious hypotension, symptoms, etc.) will receive 4-weeks supply of 160 mg oral furosemide twice daily dosing.
- B. Participants who were taking oral furosemide at study entry and tolerated the last 2-weeks of dosing will receive
 4-weeks supply of that same furosemide dose (not to exceed 320 mg/day).
- C. Participants who were taking another loop diuretic at study entry and tolerated the last 2-weeks of furosemide dosing will receive 4-weeks supply of that same furosemide dose (not to exceed 320 mg/day).
- D. Participants who did not tolerate the weeks 4 and 5 dose of furosemide will return to the prior tolerated oral furosemide dose. See below for parameters for determining intolerance.

As specified in **Section 1.3.1**, occurrence of any of the following events will end dose up-titration: 1) electrolyte abnormalities (serum potassium <3.2 mEq/L, serum magnesium <0.8 mEq/L, and/or serum corrected calcium <7 mg/dL); 2) side effects attributable to furosemide (severe or very severe rash, tinnitus, or hearing change); decrease in Inner Effectiveness of Auditory Rehabilitation (Inner EAR) instrument score by more than 10 points; and/or intradialytic systolic BP <80 mmHg that a study investigator attributes to study drug-induced hypovolemia); and/or 3) patient non-

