acceptance (defined as the patient reporting unwillingness to take the study drug). If one of these events occur, the participant will return to the prior tolerated oral furosemide dose. If one of these events occurs at the lowest administered dose, oral furosemide will be stopped and not re-started.

The window for each dose-titration period intervention/treatment visit is -4 to +4 days.

Follow-up (period 2)

Weeks 10 and 14: Participants who tolerated (i.e. no hypokalemia, serious hypotension, symptoms, etc.) and accepted furosemide in period will continue their maximally tolerated period 1 dose during the 12-weeks of follow-up. At weeks 10 and 14, they will receive additional 4-weeks supplies of this furosemide dose.

As specified in **Section 1.3.1**, if a participant has electrolyte abnormalities or other side effects attributable to furosemide in period 2 (i.e. on their period 1 maximally tolerated dose), the dose will be lowered sequentially (i.e. dose de-escalation: $160 \rightarrow 120 \rightarrow 80$ mg twice daily, or, if on alternative dosing due to prior diuretic use, decrease dose by 50%, rounded to the nearest whole tablet strength of existing (i.e. available) furosemide tablet formulations, until tolerated). If side effects persist or if the participant chooses, oral furosemide will be stopped.

Week 19: At the first weekly treatment (i.e. Monday or Tuesday) of study week 19, participants will return all unused study drug to a study coordinator.

The window for each follow-up period intervention/treatment visit is -4 to +4 days.

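### Section 7.1.4 conflicts with the dose rules in 1.2, 3.5.2 and 4.3 for serious hypotension attributed to furosemide, and its third-reduction stop fits only one rung of the diuretic-naive ladder

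*Combined protocol and SAP*

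**What the plan says.** **Dose rules in 1.2, 3.5.2 and 4.3.** One of the events that ends up-titration is "intradialytic systolic BP <80 mmHg that a study investigator attributes to study drug-induced hypovolemia". In period 1 the participant then goes back to the last dose that was tolerated. At the bottom of the range, "If one of these events occurs at the lowest administered dose, oral furosemide will be stopped and not re-started". The visit-by-visit D items in 4.3 apply the same rule when drug is dispensed. Week 2: "Participants who did not tolerate the weeks 0 and 1 dose of furosemide will stop furosemide, and it will not be restarted". Week 4: "Participants who did not tolerate the weeks 2 and 3 dose of furosemide will return to the prior tolerated oral furosemide dose"; week 6 D does likewise for the dose of weeks 4 and 5. In period 2, side effects attributable to furosemide lead to stepwise lowering: 160, 120, 80 mg twice daily for diuretic-naive participants, and 50% cuts for prior loop-diuretic users. The drug is stopped if side effects persist.

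Section 4.3 also lists serious hypotension among the things that make a dose not tolerated. It does so for escalating (Week 2 A, Week 4 A) and for continuing the same dose (Week 6 A, Weeks 10 and 14).

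**Section 7.1.4 (under 7.7).** The trigger is hypotension needing hospitalization or emergency-room treatment and not explained by sepsis, infarction or another cardiovascular event. There is no blood pressure threshold, no attribution condition and no restriction to one period. Five steps are listed in order of preference: cut other antihypertensives, raise target weight, lengthen sessions, then "Reduce dose of study drug if there are no other anti-hypertensive medications prescribed" (or if the others should not be stopped), and finally "Discontinue study medication at the 3rd dose reduction". The section closes by saying that "dose reduction or discontinuation of study drug will be directly managed by study staff in accordance with the guideline".

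**Sibling sections 7.1.1 to 7.1.3 (also under 7.7).** For potassium, magnesium and calcium these repeat the step-back-or-stop rule, for example "If the hypokalemia occurs at the lowest administered dose, furosemide will be stopped and not restarted".

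**The concern.** A single event can trigger both sets of rules: an intradialytic systolic pressure below 80 mmHg, attributed by an investigator to study drug, that sends the participant to the emergency room. One set makes a dose change mandatory. The other offers three non-drug measures first and may never reach the study drug. Section 7.1.4 makes no exception for attributed events, and no sentence ranks the rules. Followed literally, it could give an event serious enough for emergency care a weaker study-drug response than the same reading handled in the clinic, where only the 4.3 rule applies.

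The stop in step 5 is a second, separate problem. It counts reductions, whereas the rest of the protocol stops by position on the dose ladder.

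At stake is the dose a participant takes after a serious, drug-attributed event, in a dose-escalation pilot that has safety as a primary objective. In one situation, whether the participant counts as eligible for period 2 is also at stake.

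**Working it through.** **1. Do the triggers overlap?** The 4.3 event needs a reading below 80 mmHg and attribution. The 7.1.4 event needs emergency or hospital care and the absence of the listed other causes. Neither excludes the other, so an event can satisfy both.

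**2. Where the actions diverge.** They diverge when step 4 of 7.1.4 is not met, that is, when another antihypertensive is prescribed and can be cut. The diuretic-naive ladder in mg/day (3.5.2) is 2 × 80 = 160, 2 × 120 = 240 and 2 × 160 = 320.

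| Period | Dose at event (twice daily) | mg/day under 3.5.2 and 4.3 | mg/day if 7.1.4 governs and step 4 is not met | Gap (mg/day) |
|---|---|---|---|---|
| 1 | 80 mg | 0 (stop) | 160 | 160 |
| 1 | 120 mg | 160 | 240 | 80 |
| 1 | 160 mg | 240 | 320 | 80 |
| 2 | 160 mg | 240 | 320 | 80 |
| 2 | 120 mg | 160 | 240 | 80 |
| 2 | 80 mg | no lower rung; 0 if side effects persist | 160 | up to 160 |

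The gaps exist only if 7.1.4 displaces the other sections.

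**3. How long a gap could last.** In period 1 the D items require a stop or step back at weeks 2, 4 and 6, and kits hold two weeks of drug (3.5.3). The gap therefore lasts at most until the next dispensing visit. Period 2 has no equivalent D items and uses four-week kits, so an unchanged dose could last longer.

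**4. Period 2 eligibility, diuretic-naive.** From 120 or 160 mg twice daily the participant remains on drug under either rule. Only an event at 80 mg twice daily in period 1 gives stop against continue, so eligibility can differ only there.

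**5. The third-reduction stop.** Steps to a stop on the diuretic-naive ladder:
- from 160 mg: 160 → 120 → 80 → stop, 3 steps
- from 120 mg: 120 → 80 → stop, 2 steps
- from 80 mg: stop, 1 step

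The plan's third step is reproduced only from 160 mg twice daily. At 80 mg twice daily, step 4 asks for a reduction to a dose the ladder does not define.

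For prior loop-diuretic users the count depends on the starting dose. As an illustration, assume each dose is halved and the floor is the smallest tablet, 20 mg. Then 160 → 80 → 40 → 20 contains a third reduction, 80 → 40 → 20 → stop ends at the third step, and 40 → 20 → stop ends at the second. The mismatch in this step is therefore claimed only for diuretic-naive participants.

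**The case against.** The best defence is that the texts can be read together. Section 4.3 is mandatory and depends on attribution. Section 7.1.4 has no attribution condition, starts with a review of medication, target weight and volume status, and then asks the nephrologist to consider options. On that reading attributed events follow 4.3 and the rest follow 7.1.4. This is sensible, and 7.1.4 does not forbid a 4.3 reduction. But it is not written down. The closing sentence of 7.1.4 ties staff changes of study drug to its own guideline. That sentence contrasts study staff with treating clinicians and does not mention 4.3, so it does not establish that 7.1.4 overrides 4.3 either.

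A reader might infer that the serious-hypotension wording in 4.3 only blocks escalation, which would leave period 1 wholly unsettled. The text does not support this. Week 6 A and Weeks 10 and 14 use the same wording as a condition for continuing a dose, and the D items already point to a step back or a stop. That part of the defence stands and shortens the period 1 consequence.

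The step 5 stop can also be read as a cap, since it does not prohibit stopping earlier. That is fair. The lowest-dose rule and the persisting-side-effects clause allow earlier stops, and 9.2.1 lets an investigator end participation. Section 3.5.3 also withholds escalation after serious hypotension. None of these says which rule governs the dose after the event.

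The conflict case is narrow. It needs a low reading, attribution, emergency or hospital care and a reducible antihypertensive, in a group of up to 40 from which patients with frequent hypotension are excluded.

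**Conclusion.** The conflict is real and should be corrected. For serious hypotension attributed to study drug, 7.1.4 and the rules in 1.2, 3.5.2 and 4.3 prescribe different study-drug actions with no stated precedence. If 7.1.4 were followed in the diuretic-naive conflict case, the dose could remain 80 to 160 mg/day higher than under the other rules: until the next dispensing visit at most in period 1, longer in period 2. This assumes that step 4 is not met and that 7.1.4 displaces the other sections. At 80 mg twice daily in period 2, it also assumes that side effects persist. Separately, the step 5 stop matches the diuretic-naive ladder only from 160 mg twice daily and departs from the lowest-dose rule in the three electrolyte sections.

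Three stronger conclusions might be inferred and are not supported:
- *That the primary safety result is distorted.* The triggering event is counted under either rule, and participants who stop drug remain in follow-up (4.5). Primary safety incidence is unaffected.
- *That period 2 eligibility, and with it the recruitment top-up in 6.4, is broadly at risk.* For diuretic-naive participants it can differ only for an event at 80 mg twice daily.
- *That the protocol requires the weaker response.* It leaves the choice open.

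The documents give no event frequency, so the number of participants affected cannot be estimated.

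**What to change.** 1. State in 7.1.4 that an event attributed by an investigator to study drug-induced hypovolemia follows 4.3 whatever other antihypertensives are prescribed: step back or stop in period 1, sequential de-escalation in period 2, and a stop if it occurs at the lowest dose. Steps 1 to 3 remain available in addition.
2. For events not so attributed, keep the stepwise order with escalation held, as 3.5.3 already provides. Replace step 5 with: *If a study-drug reduction is indicated and the participant is already at the lowest administered dose, discontinue study medication.*
3. Make the serious-hypotension parenthesis in 4.3 (Weeks 2, 4, 6, 10 and 14) consistent with items 1 and 2.

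The cost is a few sentences of protocol wording and possibly a few more dose reductions or stops. No procedure or visit is added.
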